Minor congenital malformation	An anomaly or abnormality of body structure that is present at birth, is of prenatal origin (i.e., birth defect), poses no significant health problem in the neonatal period, and tends to have limited social or cosmetic consequences for the affected individual (CDC, 2020)	The registry defines and codes minor congenital malformations with criteria specified as defined by CDC (CDC, 2019). The same process for a djudicating MCMs will be used to a djudicate minor congenital malformations.		
Spontaneous a bortion (SAB)	An involuntary fetal loss or the expulsion of the products of conception occurring at <20 gestational weeks	Section 9.3.3 provides information on the methods used to calculate gestational age.		

Table 1. Outcome Definitions and Ascertainment

Outcome	Definition	Ascertainment
Stillbirth	As defined by the ACOG, an involuntary fetal loss occurring at ≥ 20 gestational weeks or, if gestational age is unknown, a fetus weighing ≥ 350 g(ACOG, 2020)	Section 9.3.3 provides information on the methods used to calculate gestational age.
Elective termination	A voluntary fetal loss or interruption of pregnancy that occurs for any reason, including but not limited to for the preservation of maternal health or due to fetal abnormalities	-
Preterm birth	A live birth occurring at <37 gestational weeks	Section 9.3.3 provides information on the methods used to calculate gestational age.
Small for gestational age (SGA)	Birthweight <10th percentile for sex and gestational age using standard growth charts for full and preterm live-born infants (Battaglia & Lubchenco, 1967)	For the determination of SGA, the registry will utilize the sex-specific international growth reference standards from the INTERGROWTH-21st for those born between 24 ^{0/7} and 42 ^{6/7} gestational weeks (Villar et al, 2014; Villar et al, 2016). The INTERGROWTH-21st standards are the latest a vailable global reference standards, representing contemporary information from an international, multiethnic, diverse population, and have been specifically developed for modern research.

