- Concurrent pregnancy-related maternal medical conditions or pregnancy complications, including
 - Pregnancy-induced hypertension
 - Pre-eclampsia
 - o Eclampsia
 - Gestational diabetes
 - Preterm labor
 - Placenta previa
 - Placental abruption
 - Incompetent cervix
 - Ectopic pregnancy
 - Molar pregnancy

Maternal Exposures During Pregnancy (reported by the obstetric and/or prescribing HCP)

- Exposure to CIBINQO, including indication/reason for use (FDA-approved or offlabel), dose, route, frequency, and dates/duration of exposure, if available
- Exposure to other drugs or biological products (including prescription and non-prescription drugs, dietary supplements, vaccines, known teratogens, and investigational medications), including indication/reason for use, dose, route, frequency, and dates/duration of exposure, if available
- Exposure to tobacco, alcohol, marijuana, or recreational or illicit drugs, including timing of exposure, if available

Pregnancy Outcome Information (reported by the obstetric and/or pediatric HCP)

- Pregnancy outcome (for each fetus, classified in one of the following mutually exclusive categories: SAB, stillbirth, elective termination, and live birth)
- Date of pregnancy outcome
- Gestational age at pregnancy outcome
- Fetal/infant sex
- Fetal/infant weight, length, and head circumference at pregnancy outcome

PFIZER CONFIDENTIAL Page 32 of 67

- Route of delivery (i.e., spontaneous vaginal delivery, assisted vaginal delivery, or cesarean delivery)
- 5-minute Apgar score
- Congenital malformations (major and minor) and assessment of potential contributing factors
- For a non-induced fetal loss (SAB, stillbirth), factors that may have had an impact on the fetal loss and attribution
- For elective termination, reason (e.g., finding on prenatal test, risk to mother's health, undesired pregnancy)
- Maternal weight at (just prior to) pregnancy outcome

Infant Outcome Information (reported by the pediatric HCP)

- Infant weight, length, and head circumference at birth (if not provided at pregnancy outcome) and at 4 and 12 months of age
- Achievement of the developmental milestones in each Centers for Disease Control and Prevention (CDC)-defined category (social/emotional, language/communication, cognitive, and movement/physical development) at 4 and 12 months of age
- Congenital malformations (major and minor) and assessment of potential contributing factors
- Infant death, including date and cause of death

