The outcome infant developmental delay is not listed in the table because a published reference rate is not a vailable.

Sample size calculations were performed in the PASS software for the outcomes of interest; precision is calculated as the half-width of the two-sided 95% confidence interval using the Wilson (score) method for binomial proportions.

For the secondary objective, calculations were performed to determine the achievable detectable relative risk for each outcome and a range of sample sizes. Table 4 presents by outcome the sample size (number of live births or pregnant women, depending on the outcome) required in each cohort to detect a range of RR, from 1.5 to 5.5. Sample size calculations were performed using the Fisher's exact conditional test with Walters normal approximation method, and assuming a power of 80%, a 2-sided α level of 0.05, an equal number of women in each cohort (although other sampling ratios were considered), and observed prevalence of the outcomes of interest in the unexposed cohort equivalent to reference comparator prevalence in the general population. As shown in Table 4, 265 live births in the analysis population of each cohort are needed to detect a 3-fold increase in the prevalence of MCM between cohorts, or a relative risk of 3.

Applying the same assumptions previously mentioned, to attain 265 live births per cohort, 364 pregnant women would need to be enrolled in each of the 2 cohorts of the study population, and a minimum of 728 women would need to be enrolled in the registry. This sample size will afford the study the ability to detect a 3-fold increase in the risk of the primary outcome, MCM, for the secondary analysis. Additionally, Table 5 shows that without any adjustments for multiple comparisons, this sample size will offer the study >80% power to detect a 3-fold increase in all other outcomes except stillbirth (for which the study will have 21.4% power to detect a 3-fold increase).

Outcome	Reference Prevalence	Reference Denominator	Denominator	Sampling Ratio	Sample Size Needed per Cohort to Detect Specific RR (Exposed: Unexposed)								
ez	in Non- exposed Group		(Exposed: Unexposed)	RR= 1.5	RR= 2.0	RR= 2.5	RR= 3.0	RR= 3.5	RR= 4.0	RR= 4.5	RR= 5.0	RR= 5.5	
МСМ	3.0%	CDC, 2008	Live births	1:1	2,627	796	413	265	190	146	117	97	82
SAB	11.8%	Wu et al, 2019	Pregnant women	1:1	596	177	90	57	40	30	24	19	16

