Stillbirth	0.596%	MacDorm an & Gregory, 2015	Live births and stillbirths	1:1	13610	4142	2159	1389	999	769	619	516	440
Elective termination	18.6%	Jatlaoui et al, 2019	Live births	1:1	343	100	50	31	21	15	12	9	NA ¹
Preterm birth	8.47%	Martin et al, 2021	Singleton live births	1:1	868	260	134	85	60	46	36	30	25
SGA	10.0%	By definition	Singleton live births	1:1	721	215	110	70	49	37	29	24	20
Postnatal growth deficiency	10.0%	By definition	Singleton live births	1:1	721	215	110	70	49	37	29	24	20

Table 4.	Sample Size Calculations for the Secondary Objective
----------	------------------------------------------------------

CDC = Centers for Disease Control; MCM = major congenital malformation; NA = not a vailable; reference prevalence = prevalence of outcome in general population for pregnant women of any age; RR = relative risk; SAB = spontaneous a bortion; SGA = small for gestational age.

The outcome infant developmental delay is not listed in the table because a published reference rate is not available.

Sample size calculations were performed in SAS (version 9.4) for the outcomes of interest using Fisher's exact conditional test with Walters normal approximation method, and assuming a power of 80% and a 2-sided α level of 0.05.

1 For elective termination, a relative risk of 5.5 with a reference prevalence of 18.6% in the unexposed cohort would result in an estimate above 100% in the exposed cohort.

Outcomes	Power Estimate
МСМ	80%
SAB	>80%
Stillbirth	21.4%
Elective termination	>80%
Preterm birth	>80%
SGA	>80%
Postnatal growth deficiency	>80%

Table 5.Power Calculations

MCM = major congenital malformation; SAB = spontaneous abortion; SGA = small for gestational age.The outcome infant developmental delay is not listed in the table because a published reference rate is not available.

Power calculations were performed in SAS (version 9.4) for the outcomes of interest using Fisher's exact conditional test with Walters normal approximation method, and assuming a sample size of 265 per c ohort, a relative risk of 3.0 and a 2-sided α level of 0.05.

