Spontaneous abortion (SAB)	SABs among women with pregnancy outcome data who are enrolled (and exposed, if applicable based on cohort) prior to 20 gestational weeks	Women with pregnancy outcome data who are enrolled (and exposed, if a pplicable based on cohort) prior to 20 gestational weeks				
Stillbirth	Stillbirths a mong women with pregnancy outcome data	Women with pregnancy outcome data				
Elective termination	Elective terminations among women with pregnancy outcome data	Women with pregnancy outcome data				
Preterm birth	Singleton preterm live births without MCMs among women with pregnancy outcome data who are enrolled (and exposed, if applicable based on cohort) prior to 37 gestational weeks	Singleton live births without MCMs among women with pregnancy outcome data who are enrolled (and exposed, if a pplicable based on cohort) prior to 37 gestational weeks				

Table 6.Calculation of Outcome Proportion

Outcome	Numerator	Denominator
Small for gestational age (SGA)	Singleton live births without MCMs who are SGA among women with pregnancy outcome data	Singleton live births without MCMs with weight data a mong women with pregnancy outcome data
Postnatal growth deficiency (at 4 and 12 months)	Singleton infants without MCMs who were not born preterm or SGA with postnatal growth deficiency based on weight/length/head circumference among infants with weight/length/head circumference data at the time point	Singleton infants without MCMs who were not born preterm or SGA with weight/length/head circumference data at the time point
Infant developmental delay (at 4 and 12 months)	Infants without MCMs who were not born preterm with developmental deficiency in a particular category among infants with developmental milestone data for the category at the time point	Infants without MCMs who were not born preterm with developmental milestone data for the category at the time point

 Table 6.
 Calculation of Outcome Proportion

MCM = major congenital malformation; SAB = spontaneous abortion; SGA = small for gestational age.

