As the registry will enroll women only after recognition of pregnancy and in some cases may be much later in pregnancy, there will be left truncation of the enrolled population. That is, the enrolled population of pregnant women will include women with a shortened period at risk of the outcomes of interest and exclude women who have already had certain outcomes (e.g., SAB, elective termination). To minimize the impact of this potential bias, statistical methods may be used to address left truncation, and the registry's recruitment strategy will encourage recruitment of participants as early in pregnancy as possible.

Additionally, women in the exposed cohort may differ from those in the comparator cohort in important factors that could impact pregnancy outcomes. For example, patients who seek and receive CIBINQO for moderate-to-severe AD may have more severe disease than the comparator patients, so confounding by indication will need to be carefully considered for the comparison. Furthermore, there may be misclassification of disease severity, particularly in the comparator cohort, as use of chronic systemic therapies for AD will be used as a proxy for moderate-to-severe disease. Standardized methods for assessing AD severity are not available and severity is not routinely documented in medical records.

To minimize the impact of potential confounders, the registry will record the characteristics of women in both cohorts and use statistical methods to examine and account for any differences between cohorts in the analysis. The registry will employ identical data collection and follow-up procedures across the registry cohorts to minimize any potential recording/detection bias. Although statistical methods will be used to account for confounding, it may not be possible to control for all variables (e.g., unknown) that could influence the results of the study. Therefore, residual confounding remains a possibility.

Outcome misclassification is possible, especially with regard to minor congenital malformations that may be overlooked or unreported. Although some MCMs may not be easily visible at birth, most will be apparent by 12 months of age, so misclassification of these outcomes is expected to be minimal in this registry.

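### Table 6 counts pregnancies terminated before 20 weeks as SAB-free, so the comparative SAB relative risk shifts if termination rates differ between cohorts

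*Protocol*

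**What the plan says.** - **Numerator and denominator.** Table 6 in section 9.7.2 takes as numerator "SABs among women with pregnancy outcome data who are enrolled (and exposed, if applicable based on cohort) prior to 20 gestational weeks". The denominator is all "women with pregnancy outcome data who are enrolled (and exposed, if applicable based on cohort) prior to 20 gestational weeks", with no exclusion or censoring for termination.
- **Outcome categories.** Section 9.4 has each fetus "classified in one of the following mutually exclusive categories: SAB, stillbirth, elective termination, and live birth". A terminated pregnancy therefore has outcome data and belongs in the denominator.
- **Definitions.** Table 1 in section 9.3.2 defines SAB as "An involuntary fetal loss or the expulsion of the products of conception occurring at <20 gestational weeks" and elective termination as "A voluntary fetal loss or interruption of pregnancy that occurs for any reason", the latter with no gestational limit. A termination can never enter the SAB numerator.
- **Comparison.** Section 9.7.3 compares these proportions by a crude relative risk (RR) and by a log-binomial RR with stabilized inverse probability of treatment weights (IPTW) built on baseline covariates, if sample size permits.
- **Related provisions.** Section 9.7.4 lists inverse probability of censoring weights as a possible sensitivity analysis for differential loss to follow-up. Section 9.9 says that "statistical methods may be used to address left truncation".

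**The concern.** A woman who terminates at 9 weeks is not observed through the rest of the SAB risk period, yet she contributes to the denominator as if she had passed through it without miscarrying. Table 6 regulates entry to the SAB risk set (enrolled, and exposed where applicable, before 20 weeks) but not exit from it by termination.

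None of the stated methods addresses this. IPTW acts on baseline covariates, and termination comes later. The censoring weights are tied to loss to follow-up, and a terminated pregnancy is not lost. The left-truncation methods are optional and concern late entry.

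What is at stake is the SAB comparison. Reading its RR as a drug effect on miscarriage presumes similar early termination in the two cohorts, and the registry itself sets out to compare elective termination. If exposed women terminate more often, a harmful effect is attenuated, which in a safety study errs toward reassurance.

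**Working it through.** **1. The plan's own SAB figures reproduce.** Inputs from section 9.5.2: reference SAB prevalence 11.8%, and "assuming a power of 80%, a 2-sided α level of 0.05, an equal number of women in each cohort". The Walters approximation to Fisher's exact test gives 596, 177, 90, 57 and 40 per cohort for RR 1.5, 2.0, 2.5, 3.0 and 3.5, exactly as in Table 4. The Wilson half-widths for SAB in Table 3 also match (4,000, 1,002, 446 and 162 at 1%, 2%, 3% and 5%). These figures are correct and are not in question.

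**2. Model.** Constant hazards λ (SAB) and μ (termination) over the risk period to 20 weeks:
- SAB risk if nobody terminated: 1 − e^(−λ) = 0.118, so λ = −ln(0.882) = 0.1256.
- Table 6 SAB proportion: λ/(λ+μ) × (1 − e^(−(λ+μ))).
- Proportion terminated: μ/(λ+μ) × (1 − e^(−(λ+μ))).
- Bound on the distortion, if every termination precedes any SAB: (1 − qE)/(1 − qU), where q is the termination risk in the exposed (E) and unexposed (U) cohorts.

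**3. Termination rates (assumed).** The sample-size tables use "a reference prevalence of 18.6% in the unexposed cohort", with live births as denominator. As a share of all pregnancies, live births are (1 − 0.118)/(1 + 0.186 + 0.006) = 0.740, and terminations 0.740 × 0.186 = 0.138; the example uses 13.7%. The exposed rates below are assumptions.

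**4. No drug effect, 13.7% unexposed versus 27.4% exposed.**
- μ = 0.1573 and 0.3432 give SAB proportions of 10.94% and 10.02%, so RR = 0.1002/0.1094 = 0.92.
- Bound: 0.726/0.863 = 0.84.
- Dropping terminations from the denominator: (0.1002/0.726)/(0.1094/0.863) = 1.09.

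**5. Other assumed rates, no drug effect.**

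| Terminations, unexposed vs exposed | RR | Bound |
|---|---|---|
| 13.7% vs 20.6% | 0.96 | 0.92 |
| 13.7% vs 13.7% | 1.00 | 1.00 |
| 27.4% vs 13.7% (reversed) | 1.09 | 1.19 |
| 3% vs 8% | 0.97 | 0.95 |
| 0% vs 10% | 0.95 | 0.90 |

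The last row takes 10% as the risk if no SAB occurred. Section 9.5.2 assumes 90% live births, hence about 10% for all fetal losses together, so this row is the most that assumption allows.

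**6. With a true harmful effect.** A hazard ratio of 1.5 corresponds to a risk ratio of (1 − 0.882^1.5)/0.118 = 1.45 without terminations. With terminations at 13.7% versus 27.4% it appears as 1.33. At 0% versus 10%, a true risk ratio of 1.5 appears as 1.43 (bound 1.35) and 2.0 as 1.90 (bound 1.80).

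**7. Power.** Assuming termination risks of 5% versus 20% and 265 women per cohort, power for a true RR of 1.5 falls from 44% to 27% (bound 14%), and for 2.0 from 94% to 84% (bound 66%).

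**The case against.** The primary objective is a crude proportion. The share of enrolled pregnancies that end in SAB, with terminations counted as not SAB, is exactly that, and it matches the pregnant-women denominator in Tables 3 and 4. This stands: the Table 6 row is not an error, and the point concerns only the secondary RR.

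Detailed methods are left to the SAP, the sensitivity list is open-ended, and a delayed-entry analysis would have to say how termination is handled. That is fair. But the protocol itself fixes the numerator and denominator that feed the RR, and the point concerns those.

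The rates are assumed, and the larger ones sit badly with 90% live births. Women also enroll after pregnancy recognition, so their remaining risks are lower. At 265 per cohort and 11.8% SAB, the 95% interval around an RR of 1.0 runs from about 0.63 to 1.59, wide beside a shift of 3% to 8%. This limits the weight of the point. However, Tables 3 and 4 use the higher loss rates, so the protocol does not settle on low ones.

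An imbalance would show in the elective-termination row of the same table. That is true, but seeing it does not correct the SAB RR.

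A reader might go further and infer that a drug effect on miscarriage is masked, or that the registry expects termination to differ by exposure. The protocol supports neither. It states no such expectation and gives no rates by cohort. Complete masking of an RR of 1.5 needs (1 − qE)/(1 − qU) = 1/1.5, that is, one third of exposed women terminating before any SAB could occur and none in the comparator.

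**Conclusion.** The point holds for the secondary SAB comparison and is a modest, inexpensive improvement. Table 6 is a valid crude proportion. The RR built on it mixes any effect on miscarriage with any difference in early termination: downward if exposed women terminate more often, upward if less often, and essentially not at all if rates are equal.

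Under no drug effect, the RR is about 0.92 (bound 0.84) at 13.7% versus 27.4% terminations, and about 0.95 to 0.97 at rates compatible with 90% live births. This is attenuation, not concealment. The sizes rest on assumed termination rates, constant hazards to 20 weeks, and termination unrelated to miscarriage risk; the bounds replace constant hazards by terminations that all come first. The stated SAB sample sizes are unaffected.

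**What to change.** Keep the Table 6 crude SAB row as it is. For the comparison in section 9.7.3, add:

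- an IPTW-weighted SAB analysis on the gestational-age scale to 20 0/7 weeks, with delayed entry at enrollment (or at first exposure, if later, in the exposed cohort) and censoring at elective termination;
- beside it, the cumulative incidence of SAB with termination as a competing event;
- the termination proportion by cohort.

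Do not rely on simply removing terminations from the denominator. It over-corrects (RR 1.09 under no effect in the example) and serves at most as a bound.

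Cost: one more SAB estimate to present. Date of outcome, gestational age at outcome, enrollment date and exposure dates are already on the forms (section 9.4). Censoring assumes that termination is unrelated to impending miscarriage. State this openly, because terminations for fetal abnormality or maternal health, which Table 1 includes, may violate it.

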To estimate the number of pregnant women who will need to be enrolled to result in 145 live births, several factors were considered, including the expected proportion of live births in the registry, the proportion of enrolled women expected to be exposed to CIBINQO in the first trimester, and the proportion of enrolled women expected to be excluded from the analysis population. It was assumed that 90% of enrolled women would be exposed in the first trimester, 90% of enrolled pregnancies would result in a live birth (Covington et al, 2010; Veley et al, 2020), and 10% of enrolled women would be excluded from the analysis population due to not having a diagnosis of moderate-to-severe AD, occurrence of pregnancy outcome prior to enrollment (retrospectively enrolled participants), exposure to a known teratogen or an investigational medication during pregnancy outcome data (participants lost to follow-up). Given these assumptions, to attain 145 live births per cohort, 200 pregnant women would need to be enrolled in each of the 2 cohorts of the study population, and a minimum of 400 women would need to be enrolled in the registry. This sample size will

PFIZER CONFIDENTIAL Page 35 of 67 afford the study the ability to estimate the prevalence of MCM in each cohort with $\pm 3\%$ precision with 95% confidence interval.

Outcome	Reference Prevalence	Reference	Denominator	Sample Size Needed per Cohort to Estimate Prevalence with Specified Precision								
				1%	1.5%	2%	2.5%	3%	3.5%	4%	4.5%	5%
МСМ	3.0%	CDC, 2008	Live births	1,143	521	303	201	145	111	89	73	61
SAB	11.8%	Wu et al, 2019	Pregnant women	4,000	1,779	1,002	642	446	328	252	199	162
Stillbirth	0.596%	MacDorman & Gregory, 2015	Live births and stillbirths	333	184	124	93	74	61	52	45	39
Elective termination	18.6%	Jatlaoui et al, 2019	Live births	5,815	2,584	1,453	930	645	474	363	286	232
Preterm birth	8.47%	Martin et al, 2021	Singleton live births	2,983	1,329	750	482	336	248	191	152	124
SGA	10.0%	By definition	Singleton live births	3,461	1,540	868	557	388	286	219	174	141
Postnatal growth deficiency	10.0%	By definition	Singleton live births	3,461	1,540	868	557	388	286	219	174	141

Table 3. Sample Size Calculations for the Primary Objective

CDC = Centers for Disease Control; MCM = major congenital malformation; reference prevalence = prevalence of outcome in general population for pregnant women of any age; SAB = spontaneous abortion; SGA = small for gestational age.

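### Stillbirth and elective termination are planned on one denominator (Tables 3 and 4) and analysed on another (Table 6), and the planning figure for termination is a ratio used as a proportion

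*Protocol*

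**What the plan says.** **Stillbirth.** In section 9.5.2, Tables 3 and 4 take a reference prevalence of 0.596% on live births plus stillbirths. The Table 3 row reads "Live births and stillbirths 333 184 124 93 74" for precisions of 1% to 3%. The Table 4 row reads "Live births and stillbirths 1:1 13610 4142 2159 1389" for RR 1.5 to 3.0. In section 9.7.2, Table 6 has the numerator "Stillbirths a mong women with pregnancy outcome data" and the denominator "women with pregnancy outcome data", with no gestational limit.

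**Elective termination.** Tables 3 and 4 give 18.6% with live births as the denominator. Table 4 shows RR 5.5 as not available, and its footnote 1 explains that "a relative risk of 5.5 with a reference prevalence of 18.6% in the unexposed cohort would result in an estimate above 100" per cent. Table 6 has the numerator "Elective terminations among women with pregnancy outcome data" and the same all-women denominator as stillbirth.

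**Definitions.** Table 1 places spontaneous abortion (SAB) before 20 gestational weeks and stillbirth at or after 20 weeks. Termination has no gestational limit. Section 9.4 makes SAB, stillbirth, termination and live birth mutually exclusive. In Table 6, SAB and preterm birth are limited to women enrolled (and, where relevant, exposed) before 20 and 37 weeks; stillbirth has no such window.

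**The concern.** There are two separate faults.

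First, the stillbirth denominator in Table 6 mixes pregnancies at risk of stillbirth with pregnancies that ended before stillbirth was possible. The resulting proportion depends on how many pregnancies in a cohort are lost early. If exposure, or the timing of enrolment, makes early loss differ between cohorts, the stillbirth RR moves even when the risk after 20 weeks is equal. Inverse probability of treatment weighting on baseline covariates does not correct for a denominator that depends on a later outcome.

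Second, a termination is never a live birth, so 18.6 per 100 live births is a ratio of two exclusive outcomes. Wilson intervals and Fisher's test need a proportion of a group that contains the events. The termination rows of Tables 3 and 4 therefore do not describe the proportion that Table 6 will estimate.

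**Working it through.** **Inputs, all from the protocol.** Section 9.5.2: stillbirth 0.596% of live births plus stillbirths; termination 18.6 per 100 live births; SAB 11.8% of pregnant women; 90% of enrolled pregnancies ending in live birth; 80% power, two-sided 0.05, 1:1 cohorts.

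**1. Reproduce the printed rows.**

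- Table 3: smallest n with Wilson half-width h(n) = z√[p(1−p)/n + z²/(4n²)] / (1 + z²/n) at or below the target, z = 1.96. With p = 0.186, h(645) = 0.029997, so n = 645 at ±3%, as printed. The rest of the row (5,815 down to 232) also matches. With p = 0.00596, stillbirth matches to within 1 (332 and 183 against 333 and 184, the rest exact).
- Table 4: Walters power = Φ{[asin√(p₂ − 1/2n) − asin√(p₁ + 1/2n)]·√(2n) − 1.96}. With p₁ = 0.186 this returns 343, 100, 50, 31, 21, 15, 12, 9, and then 5.5 × 0.186 = 1.023, hence the NA. With p₁ = 0.00596 it returns 13,610, 4,142, 2,159 and 1,389. All match.

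So 0.186 was used as a binomial proportion.

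**2. Convert termination to a proportion.**

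- Of live births plus terminations: 0.186 / 1.186 = 0.157.
- Of all outcomes: stillbirths per live birth = 0.00596 / 0.99404 = 0.0060. Live-birth share = (1 − 0.118) / (1 + 0.186 + 0.0060) = 0.740. Terminations = 0.186 × 0.740 = 0.138.

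**3. Recompute with the same two formulas.**

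| Termination | 18.6% (printed) | 15.7% | 13.8% |
|---|---|---|---|
| n per cohort, RR 1.5 | 343 | 425 | 497 |
| Power at n = 343, RR 1.5 | 80% | 71% | 63% |
| n per cohort, RR 3 | 31 | 39 | 47 |
| n per cohort, ±3% | 645 | 564 | 507 |
| Exposed proportion at RR 5.5 | 102.3% (NA) | 86% (n = 10) | 76% (n = 13) |

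**4. Stillbirth on the Table 6 denominator.**

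- At 90% live births: 0.90 × 0.0060 = 0.54%.
- With the component rates of step 2: 0.740 × 0.0060 = 0.44%.
- Effect on the RR, as an illustration only: assume 80% of exposed and 90% of unexposed pregnancies reach 20 weeks, with equal stillbirth risk thereafter. The apparent RR is 0.80 / 0.90 = 0.89.

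**5. Check against the 90% live-birth assumption.** At 90% live births, a ratio of 18.6 per 100 gives terminations of 0.186 × 0.90 = 0.167 of pregnancies, and 0.90 + 0.167 = 1.067 exceeds 1. The two planning assumptions cannot both hold: 90% live births leaves at most 10% for all losses together.

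**The case against.** The share of known-outcome pregnancies that end in stillbirth is a coherent quantity, and most women in that denominator are at risk. A reader might infer that Table 6 divides stillbirths by pregnancies never at risk, or that a fall in this proportion after more early loss would be purely artificial. Neither follows. The denominator only includes some such pregnancies, and with more early loss fewer pregnancies really do end in stillbirth. It remains true that this is a different quantity from the one planned, and that nothing in the protocol says the change was intended.

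A reader might also infer that the stillbirth result will be misread against 0.596%. No such comparison is planned: the comparator is the internal unexposed cohort, and reference rates serve only for sample size.

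Live births plus stillbirths is itself imperfect. It omits terminations at or after 20 weeks, which had been at risk, and it conditions on surviving early loss, which exposure may affect. That is a reason to allow pregnancies reaching 20 weeks as the alternative.

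The 0.44% and 13.8% figures imply 74% live births, whereas section 9.5.2 assumes 90%. This stands, so they are one end of a range. Section 9.5.2 also equates registry and general-population prevalence, however, so the conflict lies within the protocol.

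Finally, RR 1.5 is not a target, 343 is not an adopted sample size, and at ±3% the printed 645 errs on the safe side. Stillbirth is already declared underpowered, and 265 × 0.00596 gives about 1.6 events per cohort, so an RR shift to 0.89 is small beside the imprecision. All of this limits the consequence. It does not make the rows right. Section 9.7.3 lets the SAP modify the plans, but the protocol's own tables disagree now.

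**Conclusion.** The point holds as a minor inconsistency affecting two secondary outcomes. Planning and analysis denominators differ for both, and the termination rows and footnote 1 are wrong as written because a ratio was entered as a proportion. The stillbirth proportion is diluted from 0.596% to about 0.54% (90% live births) or about 0.44% (component rates), and its RR depends on each cohort's early loss. The share of pregnancies ending before 20 weeks is not given in the protocol, so the size of any RR shift is illustrative.

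A reader might infer that the registry is wrongly sized. The document does not support that. The targets of 200 and 364 per cohort rest on major congenital malformation (MCM) and are untouched. Termination at RR 3 needs 39 to 47 per cohort against the 265 used in Table 5, so its statement of more than 80% power stands.

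**What to change.** - **Table 6, stillbirth:** restrict the denominator to pregnancies at risk, either those reaching 20 gestational weeks or live births plus stillbirths as in Tables 3 and 4. State the same denominator in all three tables.
- **Tables 3 and 4, termination:** keep the Table 6 denominator, convert 18.6 per 100 live births to a proportion of pregnancies, relabel the denominator and recompute the row in each table.
- **Table 4, footnote 1:** correct it, since RR 5.5 becomes computable on either converted rate.
- **Section 9.5.2:** reconcile the converted termination rate with the assumed 90% live births, saying which describes the registry and which the general population.

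The cost is one Table 6 cell, two planning rows, one footnote and a sentence or two of text. Pregnancy outcome and gestational age at outcome are already collected, so no new data are needed.
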